### 8.5.3 Relationship of Adverse Events to Study Drug

The investigator will assess the potential relationship of the AE to study drug using the following descriptions.

#### Categories of attributions for “Not Related” events:

- **Definitely Not Related:** This category applies to an AE that *is clearly not related* to the investigational agent/procedure, beyond a reasonable doubt. That is, another cause of the event is most plausible; and/or a clinically plausible temporal sequence is inconsistent with the onset of the event and the exposure to study drug and/or a causal relationship is considered biologically implausible.
- **Probably Not Related:** This category applied to an AE that *is doubtfully related* to the investigational agent/procedure. That is, an alternative explanation is more likely, e.g., concomitant drug(s), concomitant disease(s), known consequences of the disease under investigation or the relationship in time suggest that a causal relationship is unlikely.

#### Categories of attributions for “Related” events:

- **Possibly Related:** This category applies to an AE that *may be related* to the investigational agent/procedure. That is the AE follows a reasonable temporal sequence from administration of the study drug and that follows a known or expected response

pattern to the suspected study drug, but that could readily have been produced by a number of other factors.

- **Probably Related:** This category applies to an AE that *is likely related* to the investigational agent/procedure. That is, the AE has a temporal relationship to the administration of the investigational agent(s) or research intervention, follows a known or suspected pattern of response, and is strongly associated with study drug exposure. An alternative explanation is less likely, e.g., concomitant drugs(s), concomitant medication(s).
- **Definitely Related:** This category applies to an AE that *is clearly related* to the investigational agent/procedure. That is, the AE is listed as a possible adverse reaction and cannot be reasonably explained by an alternative explanation, e.g., concomitant drug(s), concomitant disease(s), known consequences of the disease under investigation or the relationship in time is very suggestive (e.g., it is confirmed by dechallenge and rechallenge).

For the purposes of reporting to regulatory agencies, AEs deemed as Definitely, Probably or Possibly Related will be considered Related and those deemed Definitely Not or Probably Not Related will be considered Unrelated.

## 8.5.4 Adverse Event Reporting to Ultragenyx

### 8.5.4.1 General

All AEs (i.e. any new or worsening in severity or frequency of a preexisting condition) with onset after the subject signs consent for study participation must be promptly documented on the AE eCRF via the EDC system. The Principal Investigator is responsible for evaluating all AEs, obtaining supporting documents, and ensuring documentation of the event is adequate. Details of the AE must include severity, relationship to study drug, duration, and outcome.

All AEs will be collected from the time the subject signs informed consent through 30 days following the last dose of study drug. In addition, the Investigator should report any AE that occurs after this time period that is believed to have a reasonable possibility of being associated with study drug.

AEs ongoing at 30 days following the last dose of study drug should have a comment in the source document by the Investigator whether the event has recovered, recovered with sequelae, or stabilized.

#### **8.5.4.2 Serious Adverse Events, Serious Adverse Drug Reactions, and Requirements for Immediate Reporting**

Any SAE that occurs at any time during the study, including a clinically significantly abnormal laboratory test result that is considered serious, must be reported within 24 hours of knowledge of the event to Ultragenyx or its designee. These requirements apply equally to all subjects, regardless of the study phase or the at-risk subject's treatment assignment or dosage. The reporting requirement for SAEs is from the time of signing of the ICF through 30 days following the last study drug administration.

SAEs will be reported by completing and submitting SAE report forms to Ultragenyx or its designee. Initial SAE reports must be followed by detailed descriptions. These should include copies of hospital case records and other documents when requested. Follow-up SAE information must be submitted in a timely manner as additional information becomes available. All SAEs regardless of relationship to study drug must be followed to resolution or stabilization if improvement is not expected.

A death occurring during the study, during the per-protocol follow-up period, or within 30 days after stopping treatment with the study drug must be reported to Ultragenyx or its designee within 24 hours of knowledge of the death whether or not it is considered treatment-related.

The investigator also must notify the IRB/EC of the occurrence of the SAE, in writing, as soon as is practicable and in accordance with IRB/EC requirements and local law. A copy of this notification must be provided to Ultragenyx or its designee.

#### **8.5.4.3 Urgent Safety Reporting**

The regulations governing clinical studies state that the sponsor and investigator are required to take appropriate urgent safety measures to protect subjects against any immediate hazards that may affect the safety of subjects, and that the appropriate regulatory bodies should be notified according to their respective regulations. According to the European Union (EU) Clinical Trial Directive 2001/20/EC, "...in the light of the circumstances, notably the occurrence of any new event relating to the conduct of the trial or the development of the investigational medicinal product where that new event is likely to affect the safety of the subjects, the sponsor and the investigator shall take appropriate urgent safety measures to protect the subjects against any immediate hazard. The sponsor shall forthwith inform the competent authorities of those new events and the measures taken and shall ensure that the Ethics Committee (EC) is notified at the same time." The reporting period for urgent safety issues is the period from the signing of the ICF through 30 days following the last dose of study drug. Investigators are required to report any urgent safety measures to Ultragenyx within 24 hours.

#### **8.5.4.4 Adverse Drug Reaction Reporting**

Ultragenyx or its designee will submit suspected unexpected serious adverse reactions (SUSAR) to appropriate Regulatory Authorities (including Competent Authorities in all Member States concerned), Ethics Committees, and Investigators as per local laws and regulations. Fatal and life-threatening SUSARs will be submitted no later than 7-calendar days of first knowledge of the event and follow-up information submitted within an additional eight (8) days. All other SUSARs will be submitted within 15-calendar days of first knowledge of the event.

Principal Investigators are required to report any urgent safety matters to Ultragenyx or its designee within 24 hours. Ultragenyx or its designee will inform the Regulatory Authorities, Ethics Committees, and Investigators of any events (e.g. change to the safety profile of UX007, major safety findings) that may occur during the clinical trial that do not fall within the definition of a SUSAR but may affect the safety of subjects participating in the clinical trials, as required, in accordance with applicable laws and regulations. The reporting period for urgent safety issues is the period from the signing of the ICF through 30 days following the last dose of study drug.

The investigator will notify the IRBs/Research Ethics Boards (REB)/ECs of SAEs and urgent safety matters, in accordance with IRB/REB/EC requirements and local laws and regulations. A copy of this notification must be provided to Ultragenyx or its designee.

Non-SUSARs will be maintained in the Ultragenyx safety database and provided in annual and/or periodic reports as per local laws and regulations. Ultragenyx or its designee will prepare and submit annual safety reports and/or other aggregate periodic summary reports to Regulatory Authorities and Ethics Committees, as per local laws and regulations.

#### **8.5.4.5 Pregnancy in Subject or Partner**

Pregnancies in subjects or partners must be reported within 24 hours of knowledge of the event to Ultragenyx or its designee. The reporting period for pregnancies is the period from the signing of the ICF through 30 days following the last dose of study drug.

Reported pregnancy of a subject or a subject's partner, while participating in the study, will be monitored for the full duration and/or followed until the outcome of the pregnancy is known. In the event of a pregnancy in the partner of a subject, the Investigator should make every effort to obtain the female partner's consent for release of protected health information. Refer to the Study Reference Manual for details on the reporting procedures to follow in the event of pregnancy. Pregnancy-associated SAEs will be processed and submitted, as necessary, as per the SUSAR reporting process (Section [8.5.4.4](#)).

Protocol Number: UX007G-CL201  
Amendment 4 – 30 Nov 2015

### 8.6 Financing and Insurance

Financing and insurance for this clinical trial will be addressed in clinical trial agreements with the study site.

### 8.7 Publication Policy

Any publication or presentation by the investigator and/or the Institution based on data or results resulting from the Ultragenyx study shall only be done in strict accordance with the Publication section in the Clinical Trial Agreement executed between Ultragenyx and the Institution and/or the investigator.

STATISTICAL ANALYSIS PLAN

Title: A Randomized, Double-Blind, Placebo-Controlled, Parallel-Group Study to Assess the Safety and Efficacy of UX007 in Subjects with Glucose Transporter Type 1 Deficiency Syndrome

Protocol: UX007G-CL201

Investigational product: UX007 (triheptanoin)

Phase: 2

Sponsor: Ultragenyx Pharmaceutical Inc.
[name]
[name]

Author: PPD [REDACTED] Biostatistics

Date: 11 January 2017

Version Number: 2.0

STATISTICAL ANALYSIS PLAN

SUMMARY OF CHANGES AND RATIONALE

UX007G-CL201 Version 2.0

11 January 2017

The amended version of the Statistical Analysis Plan for UX007G-CL201 (Version 1.0, dated 17 October 2016) has been modified by Version 2.0 to clarify the primary endpoint and analysis. The major changes to the protocol are summarized below; additional minor changes have also been made for consistency and clarity but are not included in this summary.

1. Added language to the primary efficacy endpoint (Section 4.1) stating that the endpoint derivation depends on the subject seizure type at randomization.

Rationale: This change was made for clarity.

2. Revised Section 5.6 on classification of subjects at randomization by seizure type to clarify purpose of classification and that all subjects are either an observable seizures subject, an absence seizures subject, or both.

Rationale: This change was made for clarity.

3. Added Unknown (UNK) type to diary seizures classification (Section 5.7.5).

4. Added language to the primary efficacy analysis (Section 8.6.3) stating that sensitivity analyses assessing the impact of missing data will be performed.

Rationale: This change was made for clarity.

5. Added Appendix D with SAS code for the primary statistical analysis.

TABLE OF CONTENTS

TITLE PAGE.....	1
SUMMARY OF CHANGES AND RATIONALE.....	2
LIST OF ABBREVIATIONS.....	8
1 INTRODUCTION.....	10
2 STUDY OBJECTIVES.....	11
2.1 Primary Objectives.....	11
2.2 Secondary Objectives	11
2.3 Exploratory Objectives	11
3 STUDY DESIGN.....	13
3.1 Study Population	13
3.2 Dosage and Administration	13
3.3 Blinding and Randomization Methods	14
3.4 Stratification Factors.....	14
3.5 Sample Size Considerations	14
3.6 Primary Analyses	15
3.7 Data Monitoring Committee	15
4 STUDY ENDPOINTS, COVARIATES AND SUBGROUPS.....	16
4.1 Primary Efficacy Endpoint.....	17
4.2 Secondary Efficacy Endpoints	17
4.3 Exploratory Efficacy Endpoints.....	18
4.4 Safety Endpoints	20
4.5 Covariates.....	20
4.6 Subgroups.....	21
5 DEFINITIONS	21

GMFM-88	Gross Motor Function Measure-88
KD	ketogenic diet
L	Litre
LSM	Least Square Mean
MCS	Mental Component Summary Scale
MedDRA	Medical Dictionary for Regulatory Activities
NCI	National Cancer Institute Common Terminology Criteria for Adverse Events
CTCAE	
PAL	Paired Associates Learning Test
PCS	Physical Component Summary Scale
PED	paroxysmal exertional dyskinesia
PEDI-CAT	Pediatric Evaluation of Disability Inventory Computer Adaptive Test

PHS-10	physical summary score
PK	Pharmacokinetics
PPVT	Peabody Picture Vocabulary Test
PSS-10	psychosocial summary score
PT	Preferred Term
RBC	red blood cell
RCPM	Raven's Coloured Progressive Matrices
RTI	Reaction Time
SAE	Serious Adverse Event
SAP	Statistical Analysis Plan
SF-10	Short Form 10 Health Survey for Children
SF-12v2	(Medical Outcomes Study) 12-Item Short Form – version 2
SMQ	Standardized MedDRA Query
SOC	System Organ Class
SSP	Spatial Span
SWM	Spatial Working Memory
TEAE	Treatment-Emergent Adverse Event
UX007	Investigational Product/study drug, triheptanoin
WBC	white blood cell
WHO-DD	World Health Organization Drug Dictionary

1 INTRODUCTION

The purpose of this Statistical Analysis Plan (SAP) is to provide details of the statistical analyses that have been outlined within the UX007G-CL201 original protocol and all amendments through Amendment 4 dated 30 November 2015. The data collected in this study will evaluate the safety and efficacy of UX007 in subjects with glucose transporter type 1 deficiency syndrome. The primary efficacy endpoint is the reduction from baseline to week 8 in frequency of seizures.

2 STUDY OBJECTIVES

2.1 Primary Objectives

The primary objectives of the study are to:

- Evaluate the efficacy of UX007 compared to placebo as measured by the reduction from baseline to week 8 in frequency of seizures: observable generalized and partial-onset seizures measured by diary for 6 weeks prior to randomization and after 2-week titration until Week 8, and absence seizures measured by overnight electroencephalography (EEG) at baseline and Week 8
- Evaluate the safety of UX007 via adverse event (AE) rates, laboratory values, and electrocardiogram (ECG)

2.2 Secondary Objectives

The secondary objectives of the study are to:

- Evaluate the efficacy of UX007 compared to placebo, as measured by:
 - Seizure response at Week 8, defined as at least 50% reduction from baseline to week 8 in frequency of seizures
 - Change from baseline to Week 8 in cognitive function using the Cambridge Neuropsychological Test Automated Battery (CANTAB)
 - Change from baseline to Week 8 in distance walked as measured by 6MWT
 - Time to onset of paroxysmal exertional dyskinesia (PED) as measured during 6MWT from baseline to Week 8
 - Change from baseline to Week 8 in gross motor function using the Gross Motor Function Measure-88 (GMFM-88) (assessed at select sites)
- Evaluate long-term efficacy as measured by changes from baseline in frequency of seizures over time
- Evaluate the optimal dose to control seizures and impact on other clinical manifestations during the Dose Exploration Period

2.3 Exploratory Objectives

Exploratory objectives are to:

[figure not shown]
- Evaluate the effects of UX007, from baseline through Weeks 8 and 52 on:
 - Neurological function using the Columbia Neurological Score (CNS)

- Physician global impression of change in clinical status using the Clinical Global Impression - Severity scale (CGI-S) and Clinical Global Impression - Improvement scale (CGI-I)
- Receptive vocabulary using the Peabody Picture Vocabulary Test (PPVT) (assessed at select sites)
- Subject or caregiver-reported quality of life using Short Form-10™ (SF-10) Health Survey for Children or SF-12 for adults
- PK properties of UX007 and its metabolites
- Evaluate the effects of UX007, from baseline through Weeks 8 and 52 on (assessed at select sites):
 - Functional disability by caregiver report using the Pediatric Evaluation of Disability Inventory – Computer Adaptive Test (PEDI-CAT)
 - Gait, using gait analysis by computerized mat
 - Visual motor integration using the Beery-Buktenica Developmental Test of Visual Motor Integration (Beery-VMI)
 - Spatial understanding and abstract reasoning using the Raven’s Coloured Progressive Matrices (RCPM)

3 STUDY DESIGN

UX007G-CL201 is a randomized, double-blind, placebo-controlled, parallel-group study to assess the safety and efficacy of UX007 in Glut1 DS. Figure 1 provides a schematic of the study design. As background for the statistical methods presented in the SAP, this section provides an overview of the study design. This overview is a summary only. The protocol is the definitive reference for all matters discussed in what follows.

Figure 1: UX007G-CL201 Study Schema

3.1 Study Population

The study will enroll approximately 40 pediatric, adolescent, and adult subjects who are currently not on, or not fully compliant with a ketogenic or other prescribed high-fat diet. Enrolled subjects are otherwise able to maintain standard of care treatment with up to 3 antiepileptic drugs (AEDs) throughout the duration of the study.

3.2 Dosage and Administration

Dosing will be initiated using a 2-week titration schedule until the subject has reached the target of 35% of total daily calories from study drug (~1-4 g/kg/day depending on age). If a subject has not reached the target of 35% of total daily calories by the end of the 2-week titration period, dose titration should continue until the maximum tolerated dose is reached. After an 8-week double-blind Treatment Period, the open-label Extension Period will begin, wherein all subjects will be treated with UX007 through Week 52 of the study. Following the Week 26 visit, all 40 subjects will participate in a 10-week Dose Exploration Period. The dose will be titrated over 1 week down to 20% of total daily caloric intake. If there are breakthrough seizures during the down titration period, or in the opinion of the investigator there has been a worsening of symptoms prior to completion of the 4-week period, the subject may begin the up-titration phase early. After 4 weeks at the 20% dose level, the UX007 dose will then be titrated up over 1 week to 40% of total daily caloric

intake and maintained at that level for 4 weeks. If a subject cannot tolerate titrating up to the 40% dose level, the dose should be titrated to the maximum tolerated dose as determined by the Investigator. After 4 weeks at the 40% (or maximum tolerated) dose level, the subject will continue in the open-label Extension period, and maintained on a UX007 dose to be determined by the Investigator.

A complete schedule of events specific for each period of the study is found in the protocol (Section 2, Table 2.1) and repeated herein as [Appendix B](#).

3.3 Blinding and Randomization Methods

Eligible subjects will be enrolled in the study and sequentially assigned an identification number. Subjects will be assigned to investigational product or placebo treatment groups via manual randomization based on a manual randomization process developed by the Sponsor. Randomization will seek to stratify subjects based on seizure frequency reported during the 6-week baseline period. At the end of the Baseline Period, eligible subjects will be randomized in a 3:1 ratio to either UX007 or placebo. Note that the first 3 subjects PPD [REDACTED] were randomized in a 1:1 ratio because they were randomized prior to the implementation of Protocol Amendment 3.

The titration and Treatment Period (Weeks 0-8) will be conducted as a randomized, double-blind, placebo-controlled study. Double-blind conditions will be established so that neither the sponsor, subject or site personnel involved in study conduct will know the identity of a subject's treatment. Following completion of the double-blind period, all eligible subjects will receive open-label UX007 for a 44-week open-label Extension Period (Weeks 9-52) to assess long-term safety and duration of effect.

3.4 Stratification Factors

Randomization is stratified based on baseline seizure frequency of ≤ 8 vs. > 8 seizures per 4 weeks based on the seizure diary for approximately 6 weeks between the screening and randomization visits.

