4.5 Covariates

Covariates that may be incorporated into models include an appropriate associated baseline value and an indicator for whether a subject is an Absence Seizures Only Subject. Transformations will be considered for model covariates that are overly skewed.

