8.6.3 Primary Efficacy Endpoint

The primary efficacy endpoint is the reduction from baseline to week 8 in frequency of seizures (normalized to a 4-week rate): observable seizures measured for 6 weeks after 2-week titration by diary and absence seizures measured overnight by electroencephalography (EEG). Observable seizure frequency at baseline will be calculated based on approximately 6 weeks between the screening and randomization visits and observable seizure frequency at week 8 will be calculated based on approximately 6 weeks between the end of titration and the week 8 visit (see Section 5.7.1). Absence seizure frequency will be based on overnight EEG at the randomization and week 8 visits.

The primary efficacy endpoint will be derived for each subject based on subject seizure type at randomization: observable seizures from the diary will be used for Observable Seizures Subjects and absence seizures from EEG will be used for Absence Seizures Only Subjects (see Section 5.6).

The primary efficacy endpoint will be analyzed, based on the Efficacy Analysis Set, using a linear regression (ANCOVA) model as described for continuous endpoints in Section 8.6.1. Logarithmic transformations will be used for modeling. The response variable in the model will be the reduction in the natural logarithm of the seizure frequency (+ 1) from baseline to Week 8 and the baseline covariate will be the natural logarithm of the baseline seizure frequency (+ 1): observable seizures from the diary will be used for Observable Seizures Subjects and absence seizures from EEG will be used for Absence Seizures Only Subjects.

An additional covariate will be included that indicates whether the subject is an Observable Seizures Subject or an Absence Seizures Only Subject. Estimates and 90% confidence intervals of percent reduction in seizure frequency will be derived from the model for each treatment group and for the difference between groups.

Missing data will be imputed as specified in Section 7.1. Sensitivity analysis assessing the impact of missing data will be performed using the methods described in Section 7.1.

Percent reduction from baseline in frequency of seizures over the entire study period will be summarized by visit (see Section 5.7.1), and by treatment group, for subjects while taking UX007, and overall.

The following additional analyses will be performed:

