- Absence seizure response at Week 8 will be analyzed, based on the Efficacy Analysis Set, using logistic regression. The baseline covariate will be the natural logarithm of the baseline frequency (+ 1) of absence seizures.
- Change from baseline in each of the 8 CANTAB scores will be analyzed, based on the Efficacy Analysis Set – CANTAB, using GEE with identity link function. The baseline covariate will be the baseline value of the corresponding CANTAB score.
- Change from baseline in 6MWT distance traveled (in meters and percent predicted) will be analyzed, based on the Efficacy Analysis Set – 6MWT, using GEE with identity link function. The baseline covariate will be the baseline value of the corresponding 6MWT measure.
- Since a high proportion of subjects do not experience onset of PED during the 6MWT, onset of PED will be analyzed as a binary indicator for whether PED occurred (yes/no). Onset of paroxysmal exertional dyskinesia (PED) during the 6MWT (yes/no) will be analyzed, based on the Efficacy Analysis Set – 6MWT, using GEE with logistic link function. The baseline covariate will be the baseline value of the indicator for onset of PED.
- Change from baseline in GMFM-88 Total score will be analyzed, based on the Efficacy Analysis Set – GMFM-88, using GEE with identity link function. The baseline covariate will be the baseline value of GMFM-88 Total score.

Missing data will be imputed as specified in Section 7.1.

Each endpoint will be summarized by visit, by treatment group, for subjects while taking UX007, and overall.

The following additional analyses will be performed:

- An analysis will be performed using the Per Protocol Analysis Set for endpoints involving all seizures, and the Per Protocol Analysis Set – Observable Seizures for endpoints involving seizures from the diary only, the Per Protocol Analysis Set – Absence Seizures for endpoints involving seizures from EEG only, and the Per Protocol Analysis Set – CANTAB for the CANTAB endpoints (see Section 6.4).
- For seizure response, an analysis will be performed with seizure frequency at baseline and Week 8 derived for each subject based on subject seizure type at randomization: observable seizures from the diary will be used for Observable Seizures Only Subjects and absence seizures from EEG will be used for Absence Seizures Subjects (see Section 5.6).

- For endpoints involving seizures, an analysis will be performed using the alternative imputation methods described in Section 7.1.

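### The absence-seizure (EEG), CANTAB, 6MWT, PED and GMFM-88 comparison models carry no term for the seizure-frequency stratum used in randomisation, so they are mildly conservative if that stratum is prognostic

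*SAP*

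**What the plan says.** SAP 3.4 says "Randomization is stratified based on baseline seizure frequency" and defines the strata: "baseline seizure frequency of ≤ 8 vs. > 8 seizures per 4 weeks based on the seizure diary", taken over the roughly six weeks between screening and randomisation. It does not say which diary seizure codes count.

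SAP 4.5 names the terms that models may contain. They "include an appropriate associated baseline value and an indicator for whether a subject is an Absence Seizures Only Subject". The stratum is not among them, nor is it in the generic models of 8.6.1.

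For the primary ANCOVA (8.6.3), "the baseline covariate will be the natural logarithm of the baseline seizure frequency (+ 1"), and "observable seizures from the diary will be used for Observable Seizures Subjects and absence seizures from EEG will be used for Absence Seizures Only Subjects". The diary window is the one used for stratifying: "Observable seizure frequency at baseline will be calculated based on approximately 6 weeks between the screening and randomization visits". The model has one more term: "An additional covariate will be included that indicates whether the subject is an Observable Seizures Subject or an Absence Seizures Only Subject".

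In 8.6.4, seizure response uses the same two covariates as the primary model, and the two observable-seizure models use log baseline observable frequency. The two absence-seizure models use only the log EEG baseline. For CANTAB, "The baseline covariate will be the baseline value of the corresponding CANTAB score". The 6MWT, PED and GMFM-88 models follow the same pattern, each with its own baseline and nothing about seizures.

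**The concern.** Stratified randomisation balances the arms on the stratum. That makes the true sampling variance of the treatment difference smaller when the stratum is prognostic. A model without the stratum, or anything that carries its information, does not credit that balance. The between-stratum variation stays in the residual, the reported standard error is too large, and the one-sided 5% test runs below 5%. Power is lost for no gain. The stated design has about 80% power for the primary comparison with roughly 10 placebo subjects, so there is little to spare. The SAP gives no reason for the omission.

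**Working it through.** **1. The plan's own figure.** Inputs from SAP 3.5 and 3.3: difference 50, SD 55, one-sided alpha 0.05, 40 subjects at 3:1 (30 and 10). Standardised effect 50/55 = 0.909. Standard error in SD units √(1/10 + 1/30) = 0.365. Ratio 0.909/0.365 = 2.490. Power Φ(2.490 − 1.645) = 80.1% (noncentral t, 38 df: 78.8%). The stated value of approximately 80% reproduces.

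**2. Which models carry diary frequency.**

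| Week 8 models (8.6.3, 8.6.4) | Number | Seizure-diary term |
|---|---|---|
| Primary ANCOVA | 1 | log baseline, plus Absence Only indicator |
| Seizure response | 1 | same |
| Observable seizures (reduction, response) | 2 | log baseline observable frequency |
| Absence seizures (reduction, response) | 2 | none (EEG only) |
| CANTAB | 8 | none |
| 6MWT (metres, % predicted) | 2 | none |
| PED | 1 | none |
| GMFM-88 total | 1 | none |

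Uncovered: 2 + 8 + 2 + 1 + 1 = 14 of 18.

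**3. Are the first four covered?** For Observable Seizures Subjects the covariate is the stratifying variable itself, undivided and from the same window. Under SAP 5.6 anyone with observable frequency of 4 or more is an Observable Seizures Subject, so an Absence Seizures Only Subject is below 4. If the stratum counts observable types, all such subjects are in the ≤8 stratum, and the indicator identifies them. Simulation of the primary-type model: 10,000 trials, 40 subjects, 3:1 in blocks of 4 within strata. Assumed: lognormal baseline with median 10 and log SD 1.1, residual SD 0.8, treatment effect 0.80 on the log scale.
- Outcome linear in log baseline: adding the stratum moves the SE from 0.294 to 0.296 and power from 85.1% to 84.6%. Size without it is 4.9%.
- 25% Absence Only subjects: SE 0.298 to 0.300, power 84.1% to 83.2%.
- Pure step at 8, the case least favourable to the SAP: SE 0.307 to 0.297, power 82.9% to 84.9%.

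**4. Size of the loss where nothing covers the stratum.** Let the stratum shift the outcome by d residual SDs beyond the model's own covariate, with strata of equal size (both assumed). Omitting it multiplies the residual variance by 1 + d²/4, so the model SE is k = √(1 + d²/4) times the true SE. Size is Φ(−1.645k). Power is Φ(2.490 − 1.645k), borrowing the planned standardised effect because the documents give none for these endpoints.

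| d | 1 + d²/4 | k | Size | Power | Loss (points) |
|---|---|---|---|---|---|
| 0 | 1.000 | 1.000 | 5.0% | 80.1% | 0 |
| 0.25 | 1.016 | 1.008 | 4.9% | 79.7% | 0.4 |
| 0.4 | 1.040 | 1.020 | 4.7% | 79.2% | 0.9 |
| 0.5 | 1.063 | 1.031 | 4.5% | 78.6% | 1.4 |
| 0.8 | 1.160 | 1.077 | 3.8% | 76.4% | 3.7 |
| 1.0 | 1.250 | 1.118 | 3.3% | 74.2% | 5.9 |

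**5. Simulation against the formula** (40 subjects, 3:1, blocks of 4; without versus with the stratum).
- 20,000 trials, two strata of 20, effect 0.9 SD. d = 0.4: size 4.6% vs 5.0%, power 76.3% vs 77.3%. d = 0.8: 3.8% vs 4.9%, 73.1% vs 77.1%. d = 1.0: 3.2% vs 5.0%, 70.0% vs 76.9%.
- 8,000 trials. d = 0.25: power 72.1% vs 72.4%. d = 0.4: 71.2% vs 72.5%. d = 0.5: 71.8% vs 73.6%. Monte Carlo error of each figure is about √(0.72 × 0.28/8000) = 0.5 points.
- 10,000 trials, own-baseline model, stratum shift 0.4 with residual SD 0.8 (d = 0.5): SE 0.305 vs 0.296 (ratio 1.03, as in the table), size 4.5% vs 4.9%, power 82.8% vs 84.1%.

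**6. Cost of including it needlessly.** With no stratum effect, power is 76.6% without and 76.7% with the stratum in the two-strata simulation. In the primary-type model with a non-prognostic baseline it is 84.6% and 84.1%. The cost is between nothing and half a point.

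**The case against.** A reader might infer that because no model names the stratum, every efficacy analysis loses precision, including the primary one. The documents do not support that. The primary, seizure-response and observable-seizure models adjust for the same diary variable in continuous form, which normally carries at least as much information as the split at 8. In the linear case of step 3, adjusting for the stratum alone gave a larger SE (0.305) than the SAP's covariate (0.294). This part of the objection stands, with two limits. If absence codes M to P count towards the stratum, an Absence Seizures Only Subject could be in the >8 stratum while the model holds only an EEG value. And in the alternate derivation of 8.6.3, Both Seizures Subjects carry the EEG baseline although their diary frequency may lie in either stratum.

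A reader might also infer an inflated false-positive rate. Omission works the other way.

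Other points also have weight. Nothing in the documents supports a stratum effect as large as 0.8 SD on change in CANTAB, 6MWT or GMFM-88, and Protocol 7.4.3 reports that seizure frequency is unrelated to phenotypic severity. Block size and equal strata are assumptions. The process is manual, is described only as seeking to stratify, and the first three subjects were allocated 1:1, so balance and the resulting conservatism may be weaker than simulated. Only linear models were simulated. PED is sparse by the SAP's own account: at an assumed 10% event probability, an arm with all or no events arose in 39% of simulated trials, and an arm or stratum in 46%, so an extra term can make separation worse. The Week 52 models of 8.6.2 are for estimation, so a test-level argument does not reach them.

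**Conclusion.** The point holds for the 14 models with no diary term. It is conservative in direction and usually small: about 0.5 to 1.5 points of power at an assumed 0.25 to 0.5 residual SD, and 4 to 7 points (size about 3 to 4%) at 0.8 to 1.0 SD. The stratum effect is unknown, and the larger values have no support in the documents. All 14 models are secondary. For the primary ANCOVA, seizure-response and observable-seizure models the SE changes by about 1%, or about 3% if prognosis is a pure step at 8. That conclusion depends on the stratum counting observable types only, which SAP 3.4 leaves open. The primary SAS code in Appendix D is redacted, so this rests on the SAP text. The case for change is that the remedy is close to free, not that the analysis is invalid.

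**What to change.** Before unblinding, amend the SAP as follows.
- In 3.4, state which diary codes set the stratum. In 4.5, list the randomisation stratum as a covariate.
- In 8.6.1 and 8.6.4, add the stratum, or log baseline diary frequency, as a fixed covariate in the between-group models for absence-seizure reduction, CANTAB, 6MWT and GMFM-88.
- Add it to PED and the other logistic models where estimable, with a stated fallback of dropping the term under sparse data or separation.
- In 8.6.3, say that log baseline frequency stands in for the stratum in the primary ANCOVA, and add a stratum-adjusted sensitivity analysis that also covers the alternate seizure-frequency derivation.

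The cost is SAP wording, one degree of freedom per model and some risk of sparsity in the logistic models. No data collection changes, and the sample-size statement is unaffected because it rests on an unadjusted t test.
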